#### 2) Exclusion Criteria

Subjects will be considered ineligible for the study if they meet any criterion listed below:

- Is currently taking part in an evaluation of other dental restorative materials
- Has chronic periodontitis or rampant caries
- Teeth exhibiting clinical signs of periapical pathology
- Teeth with a history of self-reported preoperative pulpal problems
- Women who are pregnant (self-reported). It is standard of care to postpone routine dental procedures and radiographed until after pregnancy.
- Women who are breast feeding.
- Known allergy to resin composites or local anesthetics.
- An employee of the sponsor or members of their immediate family.
- Condition affecting salivary flow (e.g., salivary gland disorder, Sjögren's Syndrome)
- Any restorative treatment of the teeth involved in the study in the last 12 months.
- Are unwilling or unable to have dental radiographs or photographs taken of their dentition and soft tissues

- Any other condition which is the view of the investigator may affect the ability of a patient to complete the study.
- 3) Subject Withdrawal/Termination Criteria
  - Subjects who do not comply with the study procedures, such as returning for follow up visits may be withdrawn from the study.
  - Subjects who decide to stop participating in the study will be withdrawn.
  - Subjects who have a clinical pulp exposure during restoration visit will be withdrawn from study and standard of care procedures for pulp exposure and restoration placement will be followed and patient will be advised if they need further treatment and should be seen by a dentist outside the study (such as root canal therapy and/or crown).
  - Subjects who have external procedures or treatments performed on study teeth will be withdrawn from the study. However, if external treatment is only performed on one study tooth, the subject can still participate in the study and the remaining, unaffected study tooth will still be monitored for research purposes.
  - Unanticipated Adverse Device Effect

The Principal Investigator will determine whether subjects (either withdrawn subjects or subjects completing the study) are in need of additional treatment and/or follow-up observation as a result of participation in this trial (such as if a restoration fails). Additional treatment may be needed for teeth that are not included in this study, but require a restoration. Subjects and/or their insurance will be responsible for the cost of any standard of care follow-up visits or additional treatment that is not part of this study.

- E) Assessment
  - 1) Risk

The patient may expect the usual post-operative pain or sensitivity that is typically associated with the standard of care placement of dental restorations, (the risks for both groups is anticipated to be the same and are not greater than standard of care risks), including: tooth pain, bite pain/sensitivity, gingival sensitivity/tenderness/redness, discomfort from the anesthetic, or allergic reaction to the anesthetic. These events are expected to be *localized* and *transient in nature*.

Another potential risk is partial loss, chipping, or fracture of the restoration, trauma to restored or adjacent teeth, or total loss of the restoration. However, the rate of occurrence is anticipated to be very low (no higher than for other restorations).

The risk of radiographs will be kept to a minimum using standard of care procedures (lead apron, digital radiographs, etc.). It is standard of care to have bitewing radiographs annually for caries detection. It is standard of care to have periapical radiographs prior to class II restorations to ensure there are no signs of periapical pathology. These risks are not beyond standard of care risks. At radiograph time, all female subjects will be questioned regarding pregnancy. Any responding positively at the time of screening will be excluded in accordance with the inclusion/exclusion criteria. If a subject becomes pregnant during the course of the study, radiographs will be delayed until after delivery.

There is the risk of loss of confidentiality to the subject by participating in this study. This risk will be kept to a minimum by following procedures listed under confidentiality section.

#### 2) Benefits

There is no direct medical benefit to the subject for participation in this study.

3) Alternatives

Patients may choose not to participate in the study. A patient may choose to have the procedure completed at the TUSDM or their private dentist at normal clinic fees.

F) Study Procedures

#### Visit 1 (Approximately 1 hour): Screening

The subjects will be instructed to read the informed consent form (ICF). Subjects will be given ample time to have any questions answered. If a subject decides to participate, he or she will be instructed to sign the ICF. A copy of the ICF will be given to the subject.

Subject will be asked to complete demographic information and a medical history.

An oral exam, including evaluation of oral cavity, soft and hard tissues, will be completed following standard of care procedures in US dentistry using a mouth mirror and dental explorer.

Radiographs (bitewings) will be taken if none exist that are less than 1 year old and of diagnostic quality. It is within standard of care to take radiographs for caries detection if none less than 1 year old exist.

Inclusion/exclusion criteria will be evaluated.

If you are eligible to continue in the study, randomization will occur.

Periapical radiographs will be taken on the randomized teeth (if none exist that are less than 1 year old and of diagnostic quality). It is standard of care to have periapical radiographs prior to class II restorations to ensure there are no signs of periapical pathology.

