#### Randomization

A computerized randomization scheme will be developed to randomize which teeth will be in the study and which group each tooth will be in. The "sample function" in R version 3.1.2 will be used. Assignment of study teeth and treatment allocation will be recorded in each subject's Case Report Form (CRF).

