# *Visit 2 (May occur same day as Visit 1 and up to 1 month after Visit 1)(1.5-2 hours):Restoration Placement*

Medical history will be reviewed and any changes will be noted.

Eligibility and subject withdrawal criteria will be reviewed to ensure the subject still qualifies for the study.

Oral exam will occur as at Visit 1.

Intraoral photographs will be taken (photographs will only be intraoral, no facial photographs will be taken).

Sensitivity will be assessed on randomized teeth. Subjects will be asked if they experience any sensitivity on the randomized teeth. If yes, they will be asked to rate their sensitivity on a scale of 1-100.

Group 1: SonicFill™ 2 Restoration

Local anesthesia will be achieved following standard of care.

Composite shade will be chosen.

Rubber dam or other appropriate isolation will be placed following standard of care.

Tooth will be prepared for restoration following standard of care (using handpieces, burs, hand instruments, etc. as needed). All decay will be removed.

Etching and bonding will be achieved using Optibond XRT following manufacturer's instructions.

Restoration will be placed and cured using SonicFill 2 following manufacturer's instructions.

Finishing and polishing steps will be completed using Axis ProGloss Polishing System.

Group 2: Filtek™ Supreme Ultra:

Local anesthesia will be achieved following standard of care.

Composite shade will be chosen.

Rubber dam or other appropriate isolation will be placed following standard of care.

Tooth will be prepared for restoration following standard of care (using handpieces, burs, hand instruments, etc. as needed). All decay will be removed.

Etching and bonding will be achieved using Scotchbond Universal following manufacturer's instructions.

Restoration will be placed and cured using Filtek™ Supreme Ultra following manufacturer's instructions.

Finishing and polishing steps will be completed using Axis ProGloss Polishing System.

Intraoral photographs will be taken.

Restorations will be evaluated by the grading investigator (an investigator other than who placed the restorations) according to Hickel criteria (Appendix A).

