#### Radiographs

All radiographs will be taken digitally following standard of care procedures, including the subject wearing a lead apron. The radiographs used in this study contain no more radiation than would be used in a customary dental procedure. It is within standard of care to take radiographs for caries screening if radiographs that are of diagnostic quality from within the past 1 year do not exist. It is within standard of care to take radiographs yearly for evaluation after restoration placement. Radiographs will be taken at the one-year and two year recalls. In the event an adverse event is suspected, it is clinically necessary, or due to a dental emergency a radiograph may be taken at the time of the AE or emergency, but it is not the norm for this trial.

At radiograph time, all female subjects will be questioned regarding pregnancy. Any responding positively at the time of screening will be excluded in accordance with the inclusion/exclusion criteria. If a subject becomes pregnant during the course of the study, radiographs will be delayed until after delivery. Subjects unwilling or unable to have dental radiographs will be excluded from the study.

Appointment	Visit 1 Screening	Visit 2 Baseline	Visit 3 6 month	Visit 4 1 year	Visit 5 2 year
Procedures					
Informed Consent Form	Х				
Demographics	Х				
Medical History	Х	Х	Х	Х	Х
Evaluate eligibility and withdrawal criteria	х	x	х	Х	х
Oral Mucosal Tissue Examination	x	x	х	Х	Х
Radiographs	If needed			Х	Х
Randomization	Х				
Intraoral Photographs		Х	Х	Х	Х
Sensitivity Assessment		Х			
Restoration Placement		Х			
Hickel Criteria Grading		Х	Х	Х	Х
Adverse Event Assessment		X	X	Х	Х
Stipend	X	X	X	Х	Х

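### Each tooth's material is assigned at Visit 1, before the periapical films, the Visit 2 eligibility review and cavity preparation, and no described step keeps it from the screening or placing investigator

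*Combined protocol and SAP*

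**What the plan says.** **What is randomized.** The Randomization section (III.B) describes one computer-generated scheme to "randomize which teeth will be in the study and which group each tooth will be in". It adds: "Assignment of study teeth and treatment allocation will be recorded in each subject's Case Report Form (CRF".

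**When.** At Visit 1 (III.F), after the inclusion and exclusion check: "If you are eligible to continue in the study, randomization will occur". The schedule in Table 1 marks randomization at Visit 1 only.

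**What follows.**
- Still at Visit 1: "Periapical radiographs will be taken on the randomized teeth (if none exist that are less than 1 year old and of diagnostic quality". The stated purpose is to rule out periapical disease, and clinical signs of that disease exclude a tooth (III.D.2).
- Visit 2: "May occur same day as Visit 1 and up to 1 month after Visit 1". There, "Eligibility and subject withdrawal criteria will be reviewed to ensure the subject still qualifies for the study". Table 1 carries the row "Evaluate eligibility and withdrawal criteria" at Visit 2 as well as Visit 1.
- Preparation, listed separately under each material. Section III.D.3 states: "Subjects who have a clinical pulp exposure during restoration visit will be withdrawn from study".

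**Who knows.** The Blinding section covers the grader and the subject. The Personnel list (III.I.4) draws screeners, placers and graders from the same pool, the principal investigator and co-investigators; its one restriction is that nobody grades a restoration he or she placed.

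**What is reported.** The Statistical analysis section plans tables of demographics, restorations, baseline data and recall findings. It does not mention subjects who were randomized but never treated.

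**The concern.** The planned result is a within-pair comparison: for each category, the percentage of pairs in which each material does better and the percentage in which they tie. It is protected by randomization only if keeping a pair, and preparing each tooth, does not depend on which tooth drew which material. Once the material is assigned, the remaining checks include some that call for judgement about a particular tooth: reading a film, reviewing pulpal history, calling a pulp exposure. There is also a discretionary exclusion for any condition that the investigator thinks may prevent completion. If the person making such a call knows the assignment, the call can depend on it.

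The usual safeguard is to assign treatment as late as practicable and to conceal it until then. Here the study teeth must be known at Visit 1 so that films can be taken, but the material need not be.

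**Working it through.** **1. The plan's own figures.** The inputs are in the Sample size section: n = 35, a margin of error of at most 16.6%, 20% dropout and up to 44 treated.
- Margin at the worst case p = 0.5: 1.96 × √(0.25/35) = 0.1656, or 16.6%. Reproduced.
- Dropout: 35/0.80 = 43.75, rounded up to 44. Reproduced.

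The 44 counts subjects treated. No number randomized is given.

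**2. Order of steps.** First eligibility check → randomization of teeth and material → periapical films where needed → 0 days to 1 month → second eligibility review → preparation, with possible pulp-exposure withdrawal → placement. A same-day Visit 2 shortens the interval but leaves the order unchanged. No later allocation step appears anywhere.

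**3. Why equal arms do not settle it.** Take pairs in which one tooth is the harder case. By randomization, half have SonicFill 2 on the harder tooth. Let *a* be the chance that such a pair is dropped, and *b* the chance when Filtek is on the harder tooth. Among the pairs kept, the share with SonicFill 2 on the harder tooth is

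(1 − a) / [(1 − a) + (1 − b)].

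This is one half only if a = b. Each dropped pair removes one tooth per material, so the arms stay equal whatever *a* and *b* are. If the material is assigned after a given exclusion is decided, that exclusion cannot depend on it, and a = b for it by construction.

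**4. Scale.** With 35 pairs, one pair is 1/35 = 2.9 percentage points of the planned result. This shows the weight of a pair and does not estimate bias. The documents give nothing from which *a* or *b* could be set.

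**5. Precision.** The documents give no rate of loss between randomization and treatment, so a range of 0 to 15% is assumed.

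| Assumed loss | Randomize to treat 44 | Completers if only 44 randomized (44 × (1 − loss) × 0.80) | Margin of error |
|---|---|---|---|
| 0% | 44 | 35.2 | 16.5% |
| 2% | 45 | 34.5 | 16.7% |
| 5% | 47 | 33.4 | 16.9% |
| 10% | 49 | 31.7 | 17.4% |
| 15% | 52 | 29.9 | 17.9% |

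The effect on precision is small, and the plan does not cap the number randomized at 44. The issue is possible selection and how it would be reported.

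**6. What can still be changed.** Placement was planned for June 2017 to January 2018, subject to enrollment. The version date 11/2/2018 falls after January 2018 whether read as 2 November or 11 February. The 2-year visits (June to December 2019) lie ahead on either reading. On the November reading, the 1-year visits (June to December 2018) were in progress.

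**The case against.** The case on the other side has five parts.

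- **Generating an assignment is not disclosing it.** The visit text speaks of randomized teeth, which requires only that tooth selection be known at Visit 1. This stands: a reader might infer that the operator sees the material at Visit 1, and the documents do not say so. They also describe no barrier, and the allocation goes into the CRF.
- **The main eligibility check precedes randomization.** The restoration replacement policy (III.I.11) adds a pre-screen and, where pathology was found, a second examination before inclusion. Many criteria checked again at Visit 2, such as pregnancy, allergy and salivary conditions, concern the subject rather than a tooth. This stands and narrows the route, but tooth-level and discretionary criteria remain.
- **Preparation is worded identically for both materials.** True, although the common wording does not conceal the assignment from the operator.
- **Release after the Visit 2 review leaves preparation and pulp-exposure withdrawal uncovered.** This stands. Only a later release reaches them.
- **The timing change may be moot.** On the planned timeline placement was over before this version. This stands, subject to the stated possibility of slippage.

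Two stronger readings are tempting. A reader might subtract 44 treated from 100 screened and take 56 as the size of the gap. Both figures are maxima, and the difference includes ordinary failures at the first check, so it says nothing about losses after randomization. A reader might also conclude that such losses could never be traced. The CRF records the allocation, and randomization and placement are separate scheduled events. A subject with an allocation and no placement can therefore be identified. What is missing is a planned table.

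**Conclusion.** The concern holds as a modest, inexpensive design improvement. The plan fixes the material earlier than it needs to, tooth-level checks and preparation follow, and no described step keeps the assignment from those who carry them out. A pair could therefore be lost, or a tooth prepared, with knowledge of the allocation.

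No breach is shown, the arms remain balanced, and the direction and size of any bias cannot be estimated. The conclusion assumes that the single scheduled randomization covers the material as well as the teeth. The Randomization section says that it does, and no other allocation step appears.

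The undescribed custody of the code, the separation of CRF pages and the missing disposition table would, taken alone, be gaps in detail. The point rests on the order of steps, for which a better alternative is available at little cost.

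**What to change.** **Subjects not yet treated.** At Visit 1, draw only the two study teeth and take any films needed. Draw or release the tooth-to-material assignment at Visit 2, after the films are read and the eligibility review is complete. Exclusions up to that point are then independent of the allocation. The cost is opening the code chairside and keeping one separate log, with no extra films, staff or subjects. On the planned timeline this may apply to few subjects or none.

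**Optional.** Release after both cavities are prepared would also protect preparation and pulp-exposure withdrawals. It costs more, because Visit 2 is written material by material with shade chosen before preparation, so the visit would have to be reordered.

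**All subjects.** Report from the CRFs how many were randomized but not treated, with the reason for each and whether the material had been assigned by then. Keep the allocation record apart from the grading pages and closed to that subject's grader. These steps need only one table and a filing rule, and on the planned timeline the masking can still act at the 2-year visit at least.

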# *Visit 2 (May occur same day as Visit 1 and up to 1 month after Visit 1)(1.5-2 hours):Restoration Placement*

Medical history will be reviewed and any changes will be noted.

Eligibility and subject withdrawal criteria will be reviewed to ensure the subject still qualifies for the study.

Oral exam will occur as at Visit 1.

Intraoral photographs will be taken (photographs will only be intraoral, no facial photographs will be taken).

Sensitivity will be assessed on randomized teeth. Subjects will be asked if they experience any sensitivity on the randomized teeth. If yes, they will be asked to rate their sensitivity on a scale of 1-100.

Group 1: SonicFill™ 2 Restoration

Local anesthesia will be achieved following standard of care.

Composite shade will be chosen.

Rubber dam or other appropriate isolation will be placed following standard of care.

Tooth will be prepared for restoration following standard of care (using handpieces, burs, hand instruments, etc. as needed). All decay will be removed.

Etching and bonding will be achieved using Optibond XRT following manufacturer's instructions.

Restoration will be placed and cured using SonicFill 2 following manufacturer's instructions.

Finishing and polishing steps will be completed using Axis ProGloss Polishing System.

Group 2: Filtek™ Supreme Ultra:

Local anesthesia will be achieved following standard of care.

Composite shade will be chosen.

Rubber dam or other appropriate isolation will be placed following standard of care.

Tooth will be prepared for restoration following standard of care (using handpieces, burs, hand instruments, etc. as needed). All decay will be removed.

Etching and bonding will be achieved using Scotchbond Universal following manufacturer's instructions.

Restoration will be placed and cured using Filtek™ Supreme Ultra following manufacturer's instructions.

Finishing and polishing steps will be completed using Axis ProGloss Polishing System.

Intraoral photographs will be taken.

Restorations will be evaluated by the grading investigator (an investigator other than who placed the restorations) according to Hickel criteria (Appendix A).

#### Visit 3 (6 months +/- 1 month after Visit 2) (Approximately 30 mins): Follow- Up

Medical history will be reviewed and any changes will be noted.

Eligibility and subject withdrawal criteria will be reviewed to ensure the subject still qualifies for the study.

Oral exam will occur as at Visit 1.

Restorations will be evaluated by the grading investigator (an investigator other than who placed the restorations) according to Hickel criteria.

Intraoral photographs will be taken.

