#### Scotchbond™ Universal Adhesive

Scotchbond™ Universal is a single-bottle adhesive solution for all surfaces, and can be used in total-etch, self-etch or selective-etch mode for both direct and indirect restorations. Scotchbond™ Universal provides consistent bond strength to both moist and dry etched dentin, without additional primer.

- D) Subject Characteristics
  - 1) Inclusion Criteria

To be considered eligible for this study, each patient must meet all criteria listed below:

- Is at least 18 years of age
- Is willing to provide voluntary written informed consent
- Is in good medical health and able to tolerate the dental procedures
- Has 1 pair of qualifying molars or premolars that require Class II restorations. Patients with more than 2 cavities may be enrolled but the additional teeth will not be included in the study.
- Restorations must have a buccal to lingual/palatal width equal to or greater than 1/3 the distance from buccal to lingual/palatal cusp tips
- Study teeth must be in occlusal function and must also be in contact with the neighboring tooth on at least one surface
- Study teeth must be vital (i.e., free of clinical signs and symptoms of periapical pathology)

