#### Unanticipated Adverse Device Effects (UADEs)

Unanticipated adverse device effect means any serious adverse effect on health or safety or any life-threatening problem or death caused by, or associated with, a device, if that effect, problem, or death was not previously identified in nature, severity, or degree of incidence in the investigational plan or application (including a supplementary plan or application), or any other unanticipated serious problem associated with a device that relates to the rights, safety, or welfare of subjects.

UADEs will be documented in source documents and on case report forms as to onset, severity, duration, management, outcome and relatedness to the test device. UADEs will be reported to the IRB within 5 business days after learning of the effect.

- H) Ethical Standards
  - 1) Institutional Review Board (IRB) approval will be obtained prior to commencing the study. The Principal Investigator will ensure that this study is conducted in full conformance with the US Federal laws and regulations, as well as the ICH's Good Clinical Practice Guidelines.
- I) Subject Participation

1) Screening

The PI or Co-Is will conduct screening examinations to identify subjects who meet the inclusion / exclusion criteria for enrollment into the study.

2) Informed Consent

[name] and/or his representative will introduce the study.

Consenting will take place in a private clinic bay area and the patient will be given as much time as he/she needs to consider participation. The participant will be invited to include or exclude any associates (e.g., loved ones) in the consent process.

Patients will be asked to read the consent form and given ample opportunity to have their questions answered. To avoid coercion, the consenting investigator will read through the copy of the consent form with the participant section by section, making sure the participant understands each section and has an opportunity to ask questions. If at any time the participant indicates s/he is not interested in participation, the meeting will end.

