#### (b) Access

Only study personnel will have access to data. Investigators will permit monitoring, audits, and regulatory inspections and will provide direct access to study related documentation.

9) Data Safety Monitoring Plan:

The study will be monitored at appropriate intervals by a trained member of the Kavo Kerr R&D clinical Research group (or qualified designee) by means of visits to the study clinic to evaluate patient charts, study data, and study photographs. Study monitoring visits will involve review of the study status and any issues related to the study. All Informed Consent forms will be reviewed for signatures and dates. Patient charts/records will be reviewed to ensure that all enrolled subjects meet the study inclusion and exclusion criteria. All CRFs will be reviewed for completeness of data entry to ensure that the study protocol is being followed, and to perform source data verification against information contained in the patient charts. Materials will be checked for adequate storage and sufficient quantity to meet the study needs.

Study personnel will monitor this trial for all safety related issues to determine whether an unreasonable risk to subjects develops. Quality control measures include routine inspection of case report forms, source documents, data tabulations, and tracking of adverse events.

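### Could the eligibility review at Visits 3 to 5 remove subjects because of the study restoration or its outcome?

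*Combined protocol and SAP*

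**What the plan says.** Section III.F (Study Procedures) has the same sentence at Visits 2, 3, 4 and 5: "Eligibility and subject withdrawal criteria will be reviewed to ensure the subject still qualifies for the study". Table 1 repeats it as a row, "Evaluate eligibility and withdrawal criteria", marked at all five visits. Eligibility is named alongside withdrawal, and no subset of criteria is given. The Data Safety Monitoring Plan (III.I.9) adds a monitor's check: "Patient charts/records will be reviewed to ensure that all enrolled subjects meet the study inclusion and exclusion criteria".

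The entry criteria that matter here are in III.D.1 and III.D.2:

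- inclusion: "Has 1 pair of qualifying molars or premolars that require Class II restorations"
- inclusion: "Study teeth must be vital (i.e., free of clinical signs and symptoms of periapical pathology"
- exclusion: "Any restorative treatment of the teeth involved in the study in the last 12 months"
- exclusion: "Teeth exhibiting clinical signs of periapical pathology"

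In Appendix A, a non-vital tooth scores 5 under sensitivity and vitality, and apical pathology scores 5 under the radiographic examination.

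The screening section (III.I.1) describes the purpose of the screening examination as to "identify subjects who meet the inclusion / exclusion criteria for enrollment into the study".

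**The concern.** Two things look wrong.

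First, the trial's own treatment makes every subject fail the review. A restored tooth no longer needs restoring, and it has just had restorative treatment.

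Second, and more important for the statistics, a criterion that is also an outcome is being rechecked during follow-up. If staff applied the vitality or periapical criterion at a recall, a subject could leave because the restoration had done badly. The analysis compares the two restorations within each subject, so losing the subject loses the pair. If the pair was discordant, its loss moves the results towards equal performance, which is the direction of the study hypothesis. Selective loss of failures is a serious fault in a trial meant to show comparable performance, so the wording deserves a check.

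**Working it through.** **Which criteria does the restoration break, and when?** The visit windows in III.F, counted from placement at Visit 2, are compared with the 12-month look-back.

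| Visit | Window (months) | Within 12 months of placement? | Tooth still needs a Class II restoration? |
|---|---|---|---|
| 3 | 6 ± 1 = 5 to 7 | always | no |
| 4 | 12 ± 1 = 11 to 13 | only if seen before month 12 | no |
| 5 | 24 ± 2 = 22 to 26 | never | no |

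So two criteria are literally broken at Visit 3 and for part of the Visit 4 window, and one at Visit 5.

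**Does anything follow from a broken criterion?** The passages, side by side:

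- III.D.3 (withdrawal) lists non-compliance, the subject's own decision, pulp exposure at placement, external treatment of study teeth, and an unanticipated adverse device effect. Loss of an entry criterion is not listed. If only one tooth is treated externally, the subject may stay and the other tooth is followed.
- The end of III.D.3 provides for subjects who complete the study and need further care because a restoration failed.
- III.E.1 and the Radiographs section exclude for pregnancy at screening; afterwards, films are only postponed. This is the one entry criterion with an express rule for later visits.
- III.I.11 makes reimbursement after endodontic need conditional on attending every recall, which presupposes that such subjects are still in the study.
- III.F schedules Visits 4 and 5, which would be empty if Visit 3 disqualified everyone.
- At each recall the eligibility review is listed before the oral examination, any radiographs and the grading. Pathology first found that day would therefore still be graded.

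**How far do the criterion and the outcome overlap?** III.D.1 defines vital as free of periapical signs and symptoms, and III.D.2 excludes clinical signs of the same condition. In effect this is one criterion stated twice. It rests on clinical signs, whereas the apical pathology grade is radiographic, so the overlap is real but partial.

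**How large could an effect be?** The plan's own figure comes first. With n = 35, the worst-case 95% half-width is 1.96 × √(0.25/35) = 16.6 points, as stated under Sample size.

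Let e of the 35 pairs be equal in a category.

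- Removing one discordant pair changes the equal proportion from e/35 to e/34, a rise of e/(35 × 34) = e/1190. The largest value, at e = 34, is 34/1190 = 2.9 points.
- Removing a pair graded equal changes it from e/35 to (e − 1)/34, a fall of (35 − e)/1190. One lost subject therefore pushes different categories in opposite directions.
- Removing k discordant pairs raises it by at most k/35, reached only if all remaining pairs are equal. The matching half-width is then 1.96 × √(p(1 − p)/35) with p = (35 − k)/35, not the 16.6 points that apply at 50%. For k = 3 the shift is 8.6 points against a half-width of 9.3; for k = 4 it is 11.4 against 10.5.

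The loss of precision is small. With 34, 33, 32 or 31 pairs, the worst-case half-width is 16.8, 17.1, 17.3 or 17.6 points.

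**The case for a change.** The best case for a change is that the protocol limits criteria in time when it wants to. Pregnancy is tied to screening, and pulpal history is described as preoperative. The vitality and periapical criteria carry no such limit, and some others, such as willingness to have radiographs, could reasonably continue. Staff must therefore choose a subset that the text does not supply. Entry-only use is inferred, not stated, and the analysis section has no rule for keeping such a pair. About four discordant pairs lost in one category could shift the result by more than its half-width, and the remedy would cost only a few words.

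The textual part stands: apart from pregnancy, no sentence says which entry criteria apply after placement.

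The bias part does not stand. The additional loss needs a tooth whose pathology is known before a recall and still untreated, and staff who remove the subject although the withdrawal list gives no ground for it. If the tooth has already been treated, the vitality grade itself calls for replacement, so no study restoration remains to be graded whatever the eligibility review says. Treatment outside the study falls under the existing external-treatment rule. Interim radiographs are described as not the norm. The four-pair figure is a bound that needs every other pair to be equal. It does not estimate anything.

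**Conclusion.** No change is needed. The recall sentence is a drafting slip. The same words serve a clear purpose at Visit 2, which may fall up to a month after screening, and they appear to have been carried forward to visits where they no longer fit. That explanation is an inference, but the literal reading defeats itself and the rest of the protocol points one way: entry criteria govern enrollment, and III.D.3 governs removal. The monitor's check of enrolled subjects reads naturally as verification at entry.

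No bias is shown. The documents give neither a failure rate nor any sign that pairs would be lost this way. The only size available is the bound of 2.9 percentage points per discordant pair removed, in one category, with 35 pairs; where the same pair was graded equal, removing it never raises the percentage and usually lowers it.

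This conclusion assumes that staff use the withdrawal list as the ground for removal and that restorations still in place are graded at each recall. Both are the ordinary reading of the protocol.
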